This laboratory study will evaluate whether a cannabinoid enhances the analgesic efficacy of an opioid in a clinical sample of chronic pain patients, laying the foundation for a larger clinical trial evaluating the utility of cannabinoids as potentially opioid-sparing adjuvants to chronic opioid therapy for pain. Heightened CNS processing, or central sensitization (CS), occurs across numerous chronic pain conditions and is an important treatment target in its own right. While cannabinoids show initial promise as treatments or adjuncts for some chronic pain conditions and pre-clinical data suggest effects on CS, little is known about the degree to which combining cannabinoids with opioids alleviates CS-mediated chronic pain. We propose a within-subject, single exposure, double-blind, placebo-controlled, human laboratory investigation of the extent to which a cannabinoid enhances opioid analgesia in a model chronic pain population (e.g., patients with knee osteoarthritis). Human laboratory studies are an ideal method for this initial evaluation because they provide the opportunity to tightly control study drug dosing and afford high sensitivity of measurements, and enable tight control of confounding variables that may otherwise exist in clinical treatment populations and could differentially impact outcomes. This approach will minimize the number of participants needed to determine whether a positive signal exists while permitting rigorous and elegant evaluation of the study aims. Primary study outcomes will include measures of clinical pain and central sensitization, physical function, drug effects (e.g., abuse liability, adverse events, cognitive performance), and pharmacokinetic analyses. The Aims will examine the magnitude and duration of cannabinoid/opioid combination in reducing clinical pain and central sensitization; the effects on physical functioning, adverse events and indices of abuse liability; and the pharmacokinetic and pharmacodynamics profiles for the individual and combined drugs. This study will provide the most systematic and rigorous evaluation of the potential for cannabinoids to enhance analgesic effects of opioids in human subjects to date, and will do so in a relevant and generalizable clinical pain population who has CS, which makes these results more directly relevant compared to studies conducted in healthy populations. These findings will be critical to informing the efficacy and safety profile for the advancement of opioid/cannabinoid combination regimens to clinical trials with chronic pain patients.

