
2. Objectives (include all primary and secondary objectives)

Aim 1: Evaluate the magnitude and duration of cannabinoid/opioid combination to reduce clinical pain and central sensitization. We hypothesize the cannabinoid/opioid combination will increase the

magnitude and duration of analgesia in clinical pain report (Hyp1) and QST-derived central sensitization (Hyp2), relative to each drug administered alone and relative to placebo.

Aim 2: Evaluate the degree to which physical functioning is altered by the cannabinoid/opioid combination. We hypothesize that the drug combination will improve physical function (Hyp3) relative to the drugs administered alone and placebo.

Aim 3: Compare the subjective, physiological, abuse liability, and cognitive effects of the cannabinoid, opioid, and combination. We hypothesize that cannabinoids will not increase adverse events (Hyp4), or abuse liability (Hyp5: ratings of positive drug effects) relative to opioids alone and that the cannabinoid (alone and in combination with opioids) will reduce neurocognitive performance (Hyp6), relative to the opioid alone and placebo.

Aim 4: Evaluate the pharmacokinetic and pharmacodynamic profile of the cannabinoid, opioid, and the combination in OA patients. We hypothesize that the combined dose will result in an altered pharmacokinetic (Hyp7) /pharmacodynamics profile (Hyp8) compared to either drug alone.

3. Background (briefly describe pre-clinical and clinical data, current experience with procedures, drug or device, and any other relevant information to justify the research)

This laboratory study is the first step in addressing an important and timely public health problem: Can cannabinoids enhance the analgesic efficacy of an opioid and ultimately reduce opioid dosing in people with chronic pain?

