Study Design Overview: We propose to study the separate and combined effects of the FDA-approved cannabinoid dronabinol (Marinol) and the prototypical opioid hydromorphone (Dilaudid). Following telephone and screening to establish study eligibility, a cohort of **n=100** adults with knee osteoarthritis (KOA) will complete four different within-subject experimental sessions. Participants will complete one of two Phases, receiving either a 4mg or 2mg dose of hydromorphone. Randomization will be split equally across the two Phases. During each session, participants will complete baseline QST, questionnaires, and a neurocognitive battery. Oral hydromorphone will be administered in the first session. Subsequent sessions will consist of 1 of 3 conditions, and session order will be randomized and counter-balanced. Conditions will be 1) placebo; 2) oral dronabinol (10mg); and 3) combined hydromorphone and dronabinol (10mg). Measures will be repeated throughout the session to fully characterize the drug effects. Participants and staff will be kept blinded to the study medications under investigation, and participants will be informed in the consent form they may receive a combination of FDA-approved stimulants, benzodiazepines, opioids, cannabinoids, over-the-counter medications or placebo, though the participants will not actually be receiving stimulants, benzodiazepines, or over-the-counter drugs. All participants will be provided with transportation to and from the experimental sessions. Primary outcomes are measures of clinical pain, central sensitization, physical function and drug effects/adverse events. A subset of participants will undergo blood draws for pharmacokinetic (pK) profile. This will be voluntary and should aid recruitment as those that do not want an IV will still be allowed to participate in the study. We will aim to recruit 30 participants that volunteer to undergo IV/blood drawing procedures in order to characterize pK.

Phase 1: The initial Phase of this project will include hydromorphone at a dose of 4mg.

Phase 2: The second Phase of this project will include hydromorphone at a dose of 2mg in order to evaluate drug effects at a reduced opioid dose.

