Screening. Telephone Screening: Following completion of an initial phone screening, eligible participants will be scheduled for additional Screening. **Screening:** Screening will be used to obtain informed consent, and establish preliminary study eligibility. Screening may occur in-person or as a combination of virtual/in-person. Subjects will review and sign an informed consent document with a study staff member to begin the Screening visit. Virtual consenting will follow IRB guidelines for virtual consenting procedures and will occur prior to any data collection. Subjects will provide a urine sample that must test negative for illicit drugs and pregnancy (for premenopausal females), will complete a battery of measures to establish study eligibility prior to being scheduled for their first experimental session. Training for the QST protocol prior to study sessions will be completed during in-person screening activities where possible. We may also collect a saliva sample for future analyses for those that consent to this portion of the study, once allowed. Medical eligibility will be determined based on ECG, a blood sample to analyze hepatic, hematologic, and chemistry functioning, a history and physical, and a knee x-ray occurring prior to medication administration at the first Experimental Session. Eligible individuals will be asked to complete pain diaries over the course of the study to evaluate clinical pain between sessions.

Randomization: The BPRU pharmacy has no subject interaction and will manage drug randomization/blinding.

Experimental Sessions. Upon eligibility confirmation, subjects will complete four experimental study sessions (Table 1a or 1b). Sessions will begin at approximately 0800 and subjects will be asked to refrain from eating prior to the session in order to control dietary intake on the day of testing. Following provision of a negative urine sample for illicit drugs and pregnancy and consumption of a calorie-controlled breakfast (whether eaten in-person or the participant follows instructions and guidelines to eat at home), for those in the pK group, an intravenous line will be established on the non-dominant arm. After 15 minutes of rest, the first 10-14mL blood draw will be taken for those in the pK group. At

| Table 1a. Phase 1. Study Drug Dosing Subjects complete each condition | | |
|---|-------------------------|----------------------|
| Condition | Hydromorphone (Oral) | Dronabinol (Oral) |
| 1 | 4mg | 0 (placebo) |

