| Randomized Order | | |
| 2 | 0 (placebo) | 0 (placebo) |
| 3 | 0 (placebo) | 10mg |
| 4 | 4mg | 10mg |

approximately 0930 participants will complete baseline QST, physical functioning measures, and self-report measures (see below). The second 10-14mL blood draw (for those in the pK group) will be collected and then two oral capsules containing either active drug or placebo (randomized in sessions 2-4) will be administered at approximately 1100. Briefly, subjects will complete QST, physical functioning, cognitive testing, self-report, and vital sign measures (as well as blood draws for those in the pK group) at regular intervals following study drug administration. Self-report measures will include specific opioid agonist and antagonist effects, to assess whether cannabinoids

are exerting an effect on a particular category of opioid agonist symptom, and will capture whether any negative effects (e.g., nausea) occur. Frequent collection will enable evaluation of time to peak drug effects, duration of effects, and general time course of effects and is a widely used and accepted approach in laboratory studies of drug effects. During the final assessment each day, subjects will complete a Drug vs. Money Questionnaire to indicate the dollar value they would place upon the drug received⁹⁸, which is a well-accepted proxy measure of abuse liability. Study staff will document adverse events throughout the study and any subject who experiences a strongly unpleasant effect of the medications, or wishes to discontinue for any reason will be able to end participation at any time. Any subject who is experiencing strong agonist effects at the end of the session will be provided overnight accommodation in the Clinical Research Unit (CRU; which is located on our campus and with whom we have frequent collaborations); based on our experience we expect this to be rare and are budgeting for 20% of sessions to undergo a one-night CRU stay.

Measures

Pilot testing indicates it takes approximately one hour to complete the assessment battery (see Table 2).

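### Hydromorphone alone is always session 1, so combination versus hydromorphone alone is not a randomised contrast, yet the plan tests it as if it were; each session's baseline protects only in part

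*Combined protocol and SAP*

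**What the plan says.** The Study Design Overview in Section 4.a states "Oral hydromorphone will be administered in the first session". The three other conditions follow in randomised, counterbalanced order. Tables 1a and 1b and the Experimental Sessions text agree that randomisation covers sessions 2 to 4 only. Section 8.b (Protection Against Hydromorphone Risks) repeats the fixed order and gives its reason: participants who react badly to hydromorphone can be withdrawn before going further.

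The Abstract says the study will "evaluate whether a cannabinoid enhances the analgesic efficacy of an opioid". Aim 1 in Section 2 sets the combination's effect "relative to each drug administered alone and relative to placebo".

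Section 7.a specifies:
- **Hyp1 and Hyp2:** Drug x Time models, with change from baseline only if subjects vary widely at baseline. Peak change is secondary.
- **Hyp3:** Drug x Time, pre-dose to peak.
- **Hyp4 (adverse events):** a one-factor Drug model on event counts.
- **Hyp5:** the Drug vs. Money questionnaire and changes in VAS ratings.
- **Hyp6 (cognition):** Drug x Time with session number as a covariate, coding not stated. No other hypothesis has a session term.

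Drug main effects and interactions alike are interpreted by Tukey tests within mixed models, separately by Phase. Section 7 does not mention the fixed order.

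The plan has partial protections. Section 4.a says "During each session, participants will complete baseline QST, questionnaires, and a neurocognitive battery". Cognitive tasks are trained to stability at screening, and "Training for the QST protocol prior to study sessions will be completed during in-person screening activities where possible".

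**The concern.** Hydromorphone alone and session 1 are the same cell. If the first session differs from later ones because of novelty, expectation, practice or habituation to the pain tests, that difference enters every contrast with hydromorphone alone. The plan itself expects practice effects, since it adjusts for them in Hyp6.

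Whether dronabinol adds to hydromorphone on pain, adverse events, abuse liability or cognition is read from these contrasts. A first-session effect could create or hide a difference, and the plan would report the result with the same standing as combination versus placebo. Hyp4 and Hyp5 are the most exposed, because they predict no increase over the opioid. If first-session novelty raised event counts or drug ratings on hydromorphone alone, a real increase with the combination would be masked and read as support.

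Event counts have no pre-dose value. Nor does Drug vs. Money: "During the final assessment each day, subjects will complete a Drug vs. Money Questionnaire".

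**Working it through.** The documents give no session effect, SD or within-subject correlation, so there is no plan figure to reproduce and every shift below is an assumption.

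**Inputs.** Four sessions: hydromorphone alone in session 1, and the 6 orders of the other conditions in sessions 2 to 4 (Section 4.a). Per Phase, n = 64/2 = 32 completers (Section 7.c, assuming the 64 cover both Phases equally) or 100/2 = 50 (Section 4.a).

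**1. One value per session** (a raw value, a count, or a change score used as the outcome). Let s1 to s4 be the session effects. With no session term, the bias in combination minus hydromorphone alone is (s2+s3+s4)/3 − s1. A numeric covariate takes its slope from sessions 2 to 4, because the hydromorphone term absorbs session 1. It subtracts 2 × (s4−s2)/2 = s4−s2.

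| Assumed session effects | No term | Numeric session |
|---|---|---|
| Linear (0, 0.25, 0.5, 0.75) | 0.50 | 0.50 − 0.50 = 0.00 |
| Step (0, 0.5, 0.5, 0.5) | 0.50 | 0.50 − 0 = 0.50 |
| Decelerating (0, 0.4, 0.6, 0.7) | 0.57 | 0.57 − 0.30 = 0.27 |

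With n participants and residual variance σ², the contrast's variance is 2σ²/n without the term. With it, the variance is 2σ²/n + 4σ²/(2n) = 4σ²/n, which is double. With session as a factor, the design matrix (6 participants, one per order) has rank 11 for 12 columns, and the contrast cannot be estimated. Combination versus placebo and versus dronabinol have zero bias and variance 2σ²/n in every version.

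**2. Drug x Time.** Take one pre-dose and five post-dose times (assumed), with independent errors and session as a main effect. The contrast (post minus pre, combination minus hydromorphone alone) is estimable with no session term, numeric session or factor session. With 6 participants its variance is 2 × (1 + 1/5)/6 = 0.40 in all three. For a session-1 shift of 0.5 residual SD, the size of the bias is:

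| Where the shift acts | Raw post-dose | Post minus pre |
|---|---|---|
| Before and after dosing | 0.50 | 0.00 |
| After dosing only | 0.50 | 0.50 |
| Before dosing only | 0.00 | 0.50 |

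The session baselines can show a pre-dose shift. They cannot show a post-dose-only shift.

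**3. Effect on the Tukey test.** With one value per session and four conditions, the critical value is the studentised range quantile divided by √2: 2.616 for n = 32 (df 3 × 31 = 93) and 2.599 for n = 50 (df 147). Under no true difference, the test statistic is noncentral t with noncentrality shift × √n, the shift being in SDs of the paired difference. For raw values, one such SD is √2 residual SDs.

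| Shift, paired-difference SD (residual SD) | n = 32 | n = 50 |
|---|---|---|
| 0 | 1% | 1% |
| 0.2 (0.28) | 7% | 12% |
| 0.35 (0.5) | 28% | 46% |
| 0.5 (0.71) | 59% | 82% |

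The middle row uses 0.5/√2 = 0.354. The smallest significant contrast is 2.616/√32 = 0.46 or 2.599/√50 = 0.37 paired-difference SD.

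**4. Withdrawal after session 1.** In simulations with no drug effect and assumed event rates, a compound-symmetry mixed model on all available data had bias within 0.003 events when removal depended only on the modelled count. For another outcome (SD 1), with 10 to 20% removed on a correlated tolerability score, its bias ran from −0.06 to +0.04.

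**The case against.** The strongest reply is that the order is a disclosed safety measure in an early laboratory study, and that a baseline in every session plus prior training already handles session effects. Part of this stands. The order need not change, and a Drug x Time contrast does remove a shift that is equal before and after dosing. But Section 7.a makes change scores conditional for Hyp1 and Hyp2 and also interprets Drug main effects. Sensory-test training is given only where possible, and two safety and abuse-liability outcomes have no baseline.

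A reader might infer that the Hyp6 session covariate leaves the cognitive contrast unidentified, or dependent on an untestable linear trend. That holds for Drug main effects and for change scores used as the outcome. It does not hold for Hyp6's main Drug x Time contrast, which is estimable with unchanged variance under either coding.

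A reader might also infer large selection bias from withdrawals after session 1. Raw means or completers-only comparisons can be off by about 0.5 events under the assumed rates, but the plan specifies mixed models, for which the simulated bias was small.

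Finally, a reader might infer raised pre-dose pain in session 1 from the medical work-up, since the Screening text places "a history and physical, and a knee x-ray occurring prior to medication administration at the first Experimental Session". The same section starts sessions only once eligibility is confirmed, Section 8.b requires a clean ECG before enrolment, and nothing links the work-up to pain.

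**Conclusion.** The concern holds. Combination versus hydromorphone alone, the contrast that answers the lead question, is non-randomised, and the plan neither says so nor tests it differently from the randomised contrasts. Raw post-dose, Drug main-effect and no-baseline outcomes are fully exposed. Post-minus-pre contrasts are exposed only to a shift that differs before and after dosing.

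The documents do not show that a session effect exists. The rates in step 3 depend on the assumed shift and pass 5% only at about 0.17 (n = 32) or 0.13 (n = 50) paired-difference SD. They refer to the shift left after any baseline adjustment. Combination versus placebo and versus dronabinol are free of session bias in every version examined.

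**What to change.** Leave the session order as it is, and amend Section 7:

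- **(a)** State that contrasts with hydromorphone alone are non-randomised and word the enhancement claim accordingly. Identify combination versus placebo and versus dronabinol as the randomised contrasts, without substituting them for the main question.
- **(b)** For outcomes with a pre-dose value, base hydromorphone-alone contrasts on Drug x Time or change from that session's baseline, whatever the baseline variation. Give raw post-dose values alongside, and show the pre-dose difference between session 1 and later sessions.
- **(c)** For combination versus hydromorphone alone, report the session-1 shift that would remove the result. This matters most for adverse events and Drug vs. Money, where it should be on the outcome's own scale.
- **(d)** Do not treat the session covariate as correcting Drug main-effect or change-score contrasts with hydromorphone alone.
- **(e)** Report how many participants leave after session 1 and why. Analyse all available data by the planned mixed model rather than completers only, noting that bias can remain if removal depends on something other than the modelled outcome.

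The cost is SAP wording and a few extra reported analyses, with no added visits or participants. The downsides are a weaker stated claim for the main contrast and two versions of it that may disagree. Change scores also vary more than raw values when the within-session correlation r is below 0.5: the variance ratio 2(1 − r) is 1.6 at r = 0.2 and 0.4 at r = 0.8.

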Pain Testing: Subjects will complete quantitative sensory testing (QST) to comprehensively and systematically measure general pain sensitivity and central sensitization. This approach will provide data regarding the full range of analgesic effects possible, across a wide variety of psycho-physiologically-mediated, experimentally-induced measures of pain perception. Subjects will complete a baseline QST session prior to study drug administration on each experimental session day and the pain testing battery will be repeated approximately every 90 mins. The QST battery consists of threshold and tolerance, and temporal summation, and conditioned pain modulation (CPM) tests. The threshold responses will be conducted in randomized and counter-balanced order, and conditioned pain modulation will always occur last.

Threshold Responses will be assessed using thermal and pressure stimulation. *Thermal threshold:* All contact heat stimuli will be delivered using a peltier-element-based stimulator (Medoc, Israel). Two trials of heat pain threshold will be administered using a thermode that gradually increases in temperature from a pre-set baseline (31°C) until the subject indicates when the stimulus “first feels painful” (threshold, HPTh) and presses a button (which terminates the procedure) indicating that the pain is intolerable (tolerance, HPTo). *Pressure threshold:* Pressure pain thresholds (PPTh) will be determined at each of the following sites on both sides of the body using a pressure algometer (SBmedic; Sweden): the medial fat pad of the knee, patella, trapezius, and thumb. Pressure at the site is gradually increased at a steady rate and stopped when the subject indicates the stimulus is first perceived as painful. Thirty-second inter-stimulus intervals will be maintained. Trials will be averaged for one HPTh, HPTo, and PPTh measure.

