Temporal Summation (TS) of Pain will be assessed using thermal stimuli (TTS) and repetitive punctuate stimuli. Sequences of 10 heat pulses are applied and the temperature of each phasic stimulus remains the same. Within each sequence, successive thermal pulses will be delivered for a duration of approximately 0.5 sec each, with an approximately 2.5-sec inter-pulse interval. Subjects will verbally rate the perceived intensity of each thermal pulse on a 0-100 rating scale. TTS is measured as the differences between the highest rated thermal stimulus and the 1st stimulus^{57,67}. Mechanical Temporal Summation (MTS) will use a set of weighted pinprick stimulators that exert forces of 8- 512 mN. The probes are

| Table 1b. Phase 2. Study Drug Dosing Subjects complete each condition | | |
|---|-------------------------|----------------------|
| Condition | Hydromorphone (Oral) | Dronabinol (Oral) |
| 1 | 2mg | 0 (placebo) |
| Randomized Order | | |
| 2 | 0 (placebo) | 0 (placebo) |
| 3 | 0 (placebo) | 10mg |
| 4 | 2mg | 10mg |

applied perpendicular to the skin. We will apply both single stimuli and 10-stimulus trains at 1HZ, and will record subject's pain ratings (0-100). Single pinprick stimuli are alternated with trains of 10 stimuli. The difference between the pain rating to the train of stimuli and the single stimuli is then calculated as MTS¹¹⁸.

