Cold Pressor Testing and CPM: A series of procedures designed to elicit and measure endogenous inhibition of pain will be applied. Subjects will undergo a series of cold pressor tasks (i.e., the conditioning stimuli) consisting of immersion of the hand in a circulating cold water bath. During hand immersion, pressure responses or temporal summation will be re-assessed while subjects' hands remain in the cold water. Subjects may remove their hand at any time. Two minutes after finishing the first immersion, subjects will re-immerse their hand in the water, and one of these tests (pressure response or temporal summation) will be re-assessed, each separated by 2 min (the tests will be conducted in random order). A CPM Index is quantified as the average percent change (across trials) in PPT_h or TS during the cold pressor tasks relative to baseline ratings¹¹⁹. One final cold-water immersion will be performed at the conclusion of the CPM procedures. This will involve a typical cold pressor task, using immersion of the hand until the subject's tolerance is reached, with a 5-minute uninformed time limit.

CS: Temporal summation measures, CPM, and after-sensation responses to these measurements will be combined to create the CS index for use in statistical analyses for which we have previously published⁵⁷. Physical Performance Measures will objectively assess physical functioning. Patient self-report of activity relates only modestly to performance measures on standardized physical tests¹²⁰⁻¹²⁵ and physical performance under the effects of the drugs administered here are an essential test of the real-world applicability of administering such analgesic combinations in the natural environment. This set of tests will involve a Timed Up and Go (TUG) test. Stair climb (which includes hand rails) and a three-Minute Walk (3MW) test, all commonly used measures of KOA physical function¹²⁶. The TUG test measures the time it takes a subject to rise from a standard chair, walk 3m, and then return to sitting in the same chair. In the 3MW test, subjects are asked to cover as much distance as possible in 3 minutes while walking laps on a standardized indoor course. Each test will be conducted at baseline and at projected peak effect to avoid participant fatigue.

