This will be the first study to examine interactions between cannabinoids and opioids on clinical and laboratory-evoked measures of pain in a population who has chronic pain and central sensitization. The study uses a within-subject, placebo-controlled design and no data exist upon which to generate a power analysis. We have selected two primary outcomes for the measurement of analgesia: measures of conditioned pain modulation and time to hand withdraw latency in a cold presser test.

[name], a biostatistician with extensive experience analyzing within-subject laboratory tests of drug effects, conducted a revised power calculation based on new literature that employs methods similar to those of this study (Cooper et al., 2018). Sample size estimates were premised with a power of 0.8, alpha =0.05 and calculated effect sizes (Cohen, 1988). These analyses suggests a sample size ranging from 10-15 individuals would be sufficient to detect large effect sizes. Because one of our aims focuses on a sex-comparison, we originally planned to double our enrollment. Thus, our sample of 64 completers (32/sex) will yield sufficient power to evaluate direct effects of study condition on CPM and cold presser in both Phases, even at small effect size levels, and will also be sufficient to identify between-session differences on pK results¹⁴⁰.

d. Early stopping rules.

The safety of participants is the highest priority. The largest potential risk of this study is cardiovascular in nature. This notion is based upon the results of a published study that reported an increase in heart rate and blood pressure among patients exposed to the cannabinoid dronabinol who were also undergoing opioid withdrawal (of which increased heart rate and blood pressure is a known symptom). This group differs from our target population in many ways, however out of an abundance of caution in these early studies, we will use this experience to inform our safety criteria. We will monitor vital signs at all study data collection time points and will follow procedures that we have developed and successfully used in previous studies that administered drugs (e.g., cocaine) with known cardiovascular risks. Specifically, if a participant's parameters reach these thresholds, then a study physician, who will always be available via telephone, will be contacted and consulted to determine the appropriate course of action.

- Systolic blood pressure: $\geq 180\text{mm Hg}$

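### A conditioned pain modulation score taken as percent change in temporal summation is undefined at a zero baseline and wrong-signed at a negative one; absolute change avoids both

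*Combined protocol and SAP*

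**What the plan says.** The protocol's Measures section, under Cold Pressor Testing and CPM, has pressure response and temporal summation repeated while the hand is in cold water: "one of these tests (pressure response or temporal summation) will be re-assessed, each separated by 2 min". The score is then defined: "A CPM Index is quantified as the average percent change (across trials) in PPT_h or TS during the cold pressor tasks", expressed "relative to baseline ratings".

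Two kinds of TS are defined under Temporal Summation (TS) of Pain, both from ratings on a 0-100 scale. For heat: "TTS is measured as the differences between the highest rated thermal stimulus and the 1st stimulus". For pinprick: "The difference between the pain rating to the train of stimuli and the single stimuli is then calculated as MTS".

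Pressure threshold is a different sort of quantity. Under Threshold Responses, pressure is raised steadily and "stopped when the subject indicates the stimulus is first perceived as painful".

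The CPM score is used in two places. Section 7c gives the two primary analgesia outcomes as "measures of conditioned pain modulation and time to hand withdraw latency in a cold presser test". Under CS in the Measures section, "Temporal summation measures, CPM, and after-sensation responses to these measurements will be combined to create the CS index", and section 7a makes CS the outcome for Hyp2, with pain VAS for Hyp1.

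The protocol does not say whether the CPM Index rests on pressure threshold, TS or both, which TS is meant, or what is done when the baseline is zero or negative.

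**The concern.** Percent change needs a baseline that is positive and well away from zero. Pressure threshold meets that condition; a difference of two ratings does not. Someone who does not summate has a thermal score of exactly zero, and someone who rates the single pinprick above the train has a negative mechanical score. Any TS-based CPM score then has missing values in the people with least summation, reversed values in some others, and very large values where the baseline is a few points. The added variance would obscure a real drug effect on an outcome that section 7c treats as primary and that also feeds the Hyp2 index.

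**Working it through.** **Plan's own figures.** The plan gives no mean, SD or zero rate for CPM or TS, so there is none to reproduce on this point. The nearby sample-size statement in section 7c (10-15 people for large effects, power 0.8, alpha 0.05) does reproduce: a two-sided paired t test needs 15 at a standardised difference of 0.8 and 10 at 1.0.

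**Step 1: the range of each score.**
- Thermal TS = highest rating minus first rating. It is at least 0, and exactly 0 if no pulse is rated above the first.
- Mechanical TS = train rating minus single rating. It can be positive, zero or negative.

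**Step 2: the plan's formula applied to them.** Percent change = 100 x (during - before) / before.
- Before = 0: undefined.
- Before = -5, during = -10: 100 x (-5)/(-5) = +100%, although summation fell.
- A 4-point fall: -4/20 = -20%, -4/10 = -40%, -4/5 = -80%.
- A 4-point rise from 1: +4/1 = +400%.

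These follow from the definitions alone.

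**Step 3: size of the loss, drug versus placebo, wider range of inputs.** All inputs are assumptions: true TS mean 10-30 points, SD 10-15, noise SD about 4 per rating, ratings in 1- or 5-point steps, thermal TS as maximum minus first, mechanical TS as train minus single. Results:
- zero baselines: 0.1% to 8% (thermal), 0.2% to 16% (mechanical);
- negative mechanical baselines: up to 16%;
- standardised drug effect: about 0.05-0.33 with percent change, 0.15-0.49 with absolute change.

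The absolute-change figures can be checked by hand for a drug effect that lowers TS by a further 20 percentage points during immersion. Noise of about 4.24 per rating gives 4.24 x √2 = 6 per TS score. The contrast uses four scores (before and during, drug and placebo), so its noise SD is 6 x √4 = 12. The effect is then 0.20 x 10/12 = 0.17 at mean 10 and 0.20 x 30/12 = 0.50 at mean 30, close to the simulated range. A smaller drug effect lowers both rows roughly in proportion.

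**Step 4: the same contrast as power, n = 64.** Assumed: mechanical TS, SD 12, noise SD 6 per score, 5-point ratings, CPM of 15%, drug gain of 10 percentage points, paired t test.

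| TS mean | Zero / negative baselines | Percent change: mean/SD, power | Absolute change: mean/SD, power |
|---|---|---|---|
| 15 | 9.1% / 6.4% | 9.2/100.4 = 0.09, 0.11 | 1.6/12.4 = 0.13, 0.17 |
| 30 | 1.3% / 0.6% | 10.6/59.0 = 0.18, 0.30 | 3.0/12.4 = 0.24, 0.46 |

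Absolute change uses all 64 people. Percent change leaves about 54 and 62 usable pairs.

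**The case against.** - **The index may not use TS at all.** The text offers pressure threshold or TS, and a threshold-only index is free of this problem. That stands: the point applies only if TS is scored. But the text permits TS and gives no rule for it.
- **TS might be scored on the ratings themselves.** The words "relative to baseline ratings" leave this open. The definitions under Temporal Summation make a difference score the more natural reading, and the plan should say which it is.
- **Cancellation.** A reader might infer that the index averages the two modalities and so loses a real effect, since inhibition raises pressure threshold and lowers TS: +20% and -20% average to 0%. The text does not establish this. Averaging is across trials and the modalities are joined by "or"; pooling with raw signs is permitted, not required.
- **The CS index.** A reader might likewise infer that it adds components pointing in opposite directions. The protocol refers to a published method, which may already orient and standardise them. That cannot be checked from the documents, so it is a matter to confirm.
- **Loss of participants.** A reader might infer that people without summation drop out of the analysis. The battery is repeated about every 90 minutes and the analysis is a multilevel model, so an undefined value loses that observation, not necessarily the person. The usable-pair counts in step 4 come from a simple paired test and overstate the loss on this count.
- **Near-total loss of signal.** A model that floors noisy TS scores at zero produces far more zero baselines than a maximum-minus-first score does, and a before/during change is not the planned drug contrast. On the drug contrast the loss is partial.

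**Conclusion.** The concern holds for any CPM score based on TS. That percent change fails at zero and negative baselines and is unstable near zero follows from the protocol's own definitions and needs no outside figure. The size rests on assumed inputs: a standardised drug effect of about 0.05-0.33 with percent change against 0.15-0.49 with absolute change. Percent change did worse in every setting examined, but usually kept part of the effect. The two ranges overlap because they span different assumed TS levels.

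The point bears on Aim 1 whichever statement of the primary outcome governs: section 7c names CPM and cold-pressor latency, while section 7a names pain VAS and the CS index, which contains CPM. Those two statements should be reconciled. The documents do not support the further claims that the two modalities are averaged together or that the CS index is wrongly built.

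**What to change.** 1. Define the CPM Index as percent change in pressure pain threshold.
2. Score TS-based CPM separately, as absolute change in rating points (during cold pressor minus before), and state whether thermal or mechanical TS is used.
3. State that the two are not averaged.
4. Confirm in the plan that the CS index components are oriented in one direction and standardised before they are combined; if the cited method already does so, say so.
5. Reconcile sections 7a and 7c on which outcomes are primary.

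The cost is wording in the analysis plan: the same ratings are used, with no added visits or procedures. The downside is that TS-based CPM is no longer in percent, so it is less directly comparable with earlier percent-based reports.
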